In another randomized, open-label, Phase 3 trial, treatment-naïve clear cell RCC patients were randomized (2:1) to receive axitinib (N=192) or sorafenib (N=96). There was no significant difference in median PFS between patients treated with axitinib or sorafenib, 10.1 months (95% CI: 7.2, 12.1) vs 6.5 months (95% CI: 4.7, 8.3) as assessed by Independent Review Committee, respectively, with stratified hazard ratio 0.77 (95% CI: 0.56, 1.05; one sided p=0.038). The axitinib ORR assessed by an Independent Radiology Review Committee was 32%, risk ratio 2.21, (95% CI: 1.31, 3.75, stratified one-sided p=0.0006). Adverse events more common ($\geq 10\%$) with axitinib versus sorafenib were diarrhoea, hypertension, weight decrease, decreased appetite, dysphonia, hypothyroidism, and upper abdominal pain; those more common with sorafenib versus axitinib included palmar-plantar erythrodysesthesia (hand-foot) syndrome and rash, alopecia and erythema.¹³ Toxicities in this clinical trial were generally tolerable and manageable and similar to those observed in clinical trials of axitinib in pre-treated aRCC patients.¹³

Overall, the adverse events reported for axitinib in clinical studies were considered generally tolerable and manageable. For single-agent axitinib, the most common adverse events (>20% of patients) reported from 1445 cancer patients regardless of causality included diarrhea, hypertension, decrease appetite, nausea, weight decreased, dysphonia, palmar-plantar erythrodysesthesia syndrome, hypothyroidism, and proteinuria. Grade ≥ 3 events that occurred most frequently were hypertension, fatigue, and diarrhea.¹¹

Following oral administration, axitinib is rapidly absorbed (median T_{max} 2.5-4.1 hours). The plasma half life of axitinib ranges from 2.5 to 6.1 hours and steady-state is expected within 2 to 3 days of dosing. Dosing of axitinib at 5 mg twice daily resulted in approximately 1.4-fold accumulation compared to administration of a single dose. At steady state, axitinib exhibits approximately linear PK within the 1-mg to 20-mg dose range. The mean absolute bioavailability of axitinib after an oral 5 mg dose is 58%. Axitinib may be administered with or without food. Axitinib is metabolized primarily in the liver by CYP3A4/5 and to a lesser extent by CYP1A2, CYP2C19, and UGT1A1. The predominant sulfoxide and N-glucuronide metabolites in human plasma show approximately ≥ 400 -fold less in vitro potency against VEGFR-2 compared to axitinib.

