8.5. Abnormal Test Findings

The criteria for determining whether an abnormal objective test finding should be reported as an AE are as follows:

- Test result is associated with accompanying symptoms; and/or
- Test result requires additional diagnostic testing or medical/surgical intervention; and/or
- Test result leads to a change in study dosing outside of protocol-stipulated dose adjustments or discontinuation from the study, significant additional concomitant drug treatment, or other therapy; and/or
- Test result is considered to be an AE by the investigator or sponsor.

Merely repeating an abnormal test, in the absence of any of the above conditions, does not constitute an AE. Any abnormal test result that is determined to be an error does not require reporting as an AE.

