9.6.2.2. Laboratory Test Abnormalities

Laboratory test results will be graded according to the NCI CTCAE v4.03 severity grade. The frequency of patients with laboratory test abnormalities will be summarized according to the worst grade for each laboratory test.

For laboratory tests without an NCI CTCAE grade definition, results will be categorized as normal (within normal ranges), abnormal, or not done.

Shift tables will be provided to examine the distribution of laboratory abnormalities.

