9.6.2.3. Electrocardiograms

ECG measurements (an average of the triplicate measurements) will be used for the statistical analysis and all data presentations. Any data obtained from ECGs repeated for safety reasons after the nominal time points will not be averaged along with the preceding triplicates. Interval measurements from repeated ECGs will be included in the outlier analysis (categorical analysis) as individual values obtained at unscheduled time points.

QT intervals will be corrected for heart rate (QTc) using standard correction factors [ie, Fridericia's (default correction), Bazett's, and possibly a study specific factor, as appropriate]. Data will be summarized and listed QT, HR, RR, PR, QRS, QTc.

Descriptive statistics (n, mean, median, standard deviation, minimum, and maximum) will be used to summarize the absolute corrected QT interval and changes from baseline in corrected QT after treatment. Categorical analysis will be conducted for the maximum change from baseline in corrected QT and the maximum post-baseline corrected QT interval.

Shift tables will be provided for baseline vs worst on treatment corrected QT. Shift tables will also be provided for ECG abnormality at baseline vs. on treatment. Patients experiencing clinically relevant morphological ECG changes will be summarized (including frequency and percentage).

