#### **6.6.5.2. Other laboratory parameters**

All other parameters collected on the eCRF will be listed in dedicated listings presenting all corresponding collected information on the eCRF.

- Coagulation: activated partial thromboplastin time (aPTT), prothrombin time (PT), international normalized ratio (INR), and PTT.
- Urinalysis: all urinalysis parameters, including protein, glucose, blood and albumin
- Other parameters: hormone, and immunology parameters
- Pregnancy test

The listings of laboratory results will be provided for all laboratory parameters. The listings will be sorted by parameters and assessment dates or visits for each patient. Laboratory values that are outside the normal range will also be flagged in the data listings, along with corresponding normal ranges. A listing of CTCAE grading will also be generated for those laboratory tests.

In addition, listings of abnormal values will be provided for hematology, chemistry, urinalysis, coagulation parameters. If there is at least one abnormal assessment for any parameter, all the data for that laboratory parameter will be included into the listing.

For all tests not mentioned above but present in the clinical data, a listing of patients with at least one result for the relevant test will be provided.

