## ECG Summaries

The following analyses will be performed for each applicable ECG parameters (RR, PR, QRS, QT, ventricular rate -denoted as HR in what follows-, and QTc) by treatment group, during the on-treatment period. The denominator to calculate percentages for each category is the number of patients evaluable for the category

- Pearson correlation between QT and HR, QTc (QTcB, QTcF and, if applicable, QTcP) and HR using individual (non-averaged) baseline assessments
- For each of the ECG parameters (HR, and QT, QTc, QRS, PR intervals), descriptive statistics at baseline, at each post-baseline time point and changes from baseline at each post-baseline time point
- Frequency (number and percentage) of patients with notable ECG values according to the following categories:
  - QT/QTc increase from baseline >30 ms, >60 ms
  - QT/QTc > 450 ms, > 480 ms, > 500 ms
  - HR  $\leq$  50 bpm and decrease from baseline  $\geq$  20 bpm
  - HR  $\geq$  120 bpm and increase from baseline  $\geq$  20 bpm
  - PR  $\geq$  220 ms and increase from baseline  $\geq$  20 ms
  - QRS  $\geq$  120 ms

Patients with notable ECG interval values and qualitative ECG abnormalities will be listed for each patient and time point and the corresponding notable values and abnormality findings will be included in the listings.

Unscheduled ECG measurements will not be used in computing the descriptive statistics for change from baseline at each post-baseline time point. However, they will be used in the analysis of notable ECG changes and the shift table analysis of notable QT parameters.

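### The SAP only lists urine protein, coagulation and qualitative ECG abnormalities, although the protocol promises frequencies and shift tables for them

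*SAP*

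**What the plan says.** **Laboratory, protocol.** Section 9.6.2.2 makes three commitments:

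- for graded results, "The frequency of patients with laboratory test abnormalities will be summarized according to the worst grade for each laboratory test";
- for the rest, "For laboratory tests without an NCI CTCAE grade definition, results will be categorized as normal (within normal ranges), abnormal, or not done";
- for abnormal results overall, tables of shifts.

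None is limited to hematology and chemistry. Table 8 in Section 7.1.3 includes urinalysis (protein, glucose, blood) and coagulation (PT, INR, and PTT or aPTT) among the required tests. Section 2.2 makes CTCAE-graded laboratory abnormalities a secondary endpoint, and SAP 3.2.1 repeats this.

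**Laboratory, SAP.** Section 6.6.5.1 applies the worst-grade and shift tables to a closed list of hematology and chemistry tests, and restricts the summaries of ungraded tests in the same way. Section 6.6.5.2 covers what is left: "All other parameters collected on the eCRF will be listed in dedicated listings presenting all corresponding collected information on the eCRF". Coagulation and all urinalysis parameters are named there. The section adds out-of-range flags, listings of abnormal values and a listing of CTCAE grades, but no table.

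**ECG.** Protocol 9.6.2.3 states: "Shift tables will also be provided for ECG abnormality at baseline vs. on treatment". It also promises a number and percentage of patients with clinically relevant morphological change. SAP 6.6.7 says instead: "Patients with notable ECG interval values and qualitative ECG abnormalities will be listed for each patient and time point".

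**The concern.** Someone who knows only the protocol would expect tables that the SAP does not plan. Among the laboratory tests the gap matters most for urine protein. In Section 1.2.2.2 the protocol's list of the most common events with single-agent axitinib ends with "palmar-plantar erythrodysesthesia syndrome, hypothyroidism, and proteinuria". Table 5 (Section 5.3.5.3) places proteinuria in its CTCAE grade column and attaches an axitinib action to a 24-hour protein of 2 g or more. The trial therefore expects this toxicity, grades it and acts on it, yet plans no laboratory count, percentage or shift for it.

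The shift is relevant because patients may enter with some proteinuria: inclusion criterion 9b admits a dipstick of 2+ or more if the 24-hour protein is below 2 g. Without a table by baseline category, new and pre-existing proteinuria cannot be separated in the summarized laboratory data.

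**Working it through.** No arithmetic applies. The check sets the two documents side by side.

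| Item | Protocol | SAP |
|---|---|---|
| Hematology, chemistry | Worst grade or normal/abnormal/not done; shift tables (9.6.2.2) | Tabulated, with shifts (6.6.5.1) |
| Urinalysis, including protein | Same commitment; required test (Table 8) | Listings only (6.6.5.2) |
| Coagulation | Same commitment; required test (Table 8) | Listings only (6.6.5.2) |
| ECG intervals and rate | Descriptive statistics, categories, QTc shift table (9.6.2.3) | Descriptive statistics, number and percentage by category; a shift table for notable QT parameters is mentioned (6.6.7) |
| ECG abnormality, baseline versus on treatment | Shift table (9.6.2.3) | Listed (6.6.7) |
| Clinically relevant morphological change | Number and percentage (9.6.2.3) | Listed (6.6.7) |

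Four rows fall short: two laboratory families and two ECG summaries. The ECG gap is independent of the laboratory gap, and ECG findings are not among the secondary endpoints listed in Protocol 2.2.

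The next question is whether another planned table supplies the proteinuria rate.

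1. SAP 6.6.1.1 tabulates treatment-emergent adverse events by preferred term and worst grade, so proteinuria is counted there if it is reported as an adverse event.
2. Protocol 8.5 gives four alternative criteria for reporting an abnormal result. The one on dosing reads "Test result leads to a change in study dosing outside of protocol-stipulated dose adjustments or discontinuation from the study", so an axitinib change that Table 5 itself prescribes does not by itself meet that criterion.
3. Another criterion covers results that need further diagnostic testing. A dipstick of 2+ or more requires a 24-hour collection (Table 5, Table 8). A patient who reaches 2 g per 24 hours has therefore already had that extra test and meets this criterion on its plain words.
4. A dipstick of 1+, which Table 5 labels Grade 1, requires no further test. It can remain outside the adverse event data unless it has symptoms or the investigator or sponsor judges it an event.
5. The adverse event tables count events that start or worsen on treatment (SAP 3.5.1). They do not show the category from which a patient started.

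So the adverse event tables should usually capture proteinuria that triggers a 24-hour collection. They do not give a rate based on the laboratory results, and they give no shift from baseline.

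**The case against.** The best defence has four parts.

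- **The change is allowed.** Protocol Section 9 and SAP Section 2 both let the SAP modify the protocol's plans, and only major changes to the primary endpoint or its analysis need an amendment. This stands. The SAP's version history is redacted, so the lack of a visible reason cannot be held against the sponsor either.
- **Adverse event tables already cover the important cases.** For proteinuria that needs a 24-hour collection this largely stands, as steps 1 to 3 of the working show. It does not supply the shift from baseline or the low-grade results.
- **The data remain visible.** The listings carry flags and grades, and with about 55 patients projected they could be counted by hand. That is true, but a count made later from a listing is not a planned summary with a defined denominator.
- **Coagulation is hard to tabulate.** The documents do not reproduce CTCAE grades for INR or aPTT, and after amendment 4 coagulation is tested only when clinically indicated. Both points stand, and they shape the fix. Protocol 9.6.2.2 already provides for ungraded tests, so neither point justifies having no table.

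On ECGs, the SAP keeps number and percentage for QT/QTc, heart rate, PR and QRS categories. Only the two qualitative summaries are missing.

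**Conclusion.** The mismatch is real and modest. As written, the SAP leaves part of a named secondary endpoint without the summary that the protocol promises, including for a toxicity that the protocol grades and acts on. It also drops two promised ECG summaries. The loss is the laboratory-based rate and the shift from baseline. This rests on the visible text of both documents and on investigators applying Protocol 8.5 as written.

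A reader might infer more, and the documents do not support it:

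- **That proteinuria gets no rate at all.** The adverse event tables should usually provide one.
- **That the protocol's figure of more than 20% gives the number of patients missed.** That figure is an adverse event rate. Applied to the planned 40 or 55 patients, it would describe what adverse event reporting captures, not what it omits.
- **That choice of the recommended phase 2 dose is compromised.** Protocol 3.4 directs attention to discontinuation for treatment-related adverse events, which SAP 6.6.1.4 tabulates. SAP Section 6 records that dose finding was complete and that only DL1, with and without lead-in, is studied, so no comparison between dose levels is lost.

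**What to change.** Amend the SAP and keep all listings.

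1. **Urine protein (6.6.5.1).** Add worst on-treatment dipstick category by baseline category. Alongside it, give the number of patients with 24-hour protein below 2 g and at 2 g or more, using all patients with an on-treatment urinalysis as the denominator. State how many had a 24-hour collection, because it is done only after a raised dipstick.
2. **Coagulation (6.6.5.1).** Tabulate by worst CTCAE grade where a grade exists, otherwise as normal/abnormal/not done, with a shift from baseline.
3. **ECG (6.6.7).** Add the baseline versus on-treatment shift table for ECG abnormality, and the number and percentage of patients with clinically relevant morphological change.

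The cost is some SAP wording and a few tables from data already collected, with no protocol amendment. The coagulation table will be sparse after amendment 4.

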#### **6.6.6. Vital signs**

Weight for the purposes of dose calculation will be recorded at screening and within 3 days pre-dose Day 1 of each cycle. Height will be measured at screening only.

Vital sign summaries will include all vital sign assessments from the on-treatment period. All vital sign assessments will be listed, and those collected outside the on-treatment period will be flagged in the listing.

All vital sign parameters will be summarized using descriptive statistics (mean, SD, median, Q1, Q3, minimum, and maximum) of actual values and changes from baseline for each visit over time. End of Treatment visit will be summarized separately. The changes computed will be the differences from baseline.

### 6.6.7. Electrocardiogram

ECG summaries will include all ECG assessments from the on-treatment period. All ECG assessments will be listed, and those collected outside the on-treatment period will be flagged in the listing. QTcB and QTcF will be derived based on RR and QT (see below). The average of the replicate measurements will be determined after the derivation of the individual parameter at each time point.

#### Selecting Primary QT Correction for Heart Rate

The analysis of QT data is complicated by the fact that the QT interval is highly correlated with heart rate. Because of this correlation, formulas are routinely used to obtain a corrected value, denoted QTc, which is independent of heart rate. This QTc interval is intended to represent the QT interval at a standardized heart rate. Several correction formulas have been proposed in the literature. For this analysis we will use some of those methods of correction, as described below. The QT interval corrected for heart rate by the Bazett's formula, QTcB, is defined as

$$QTcB = \frac{QT}{\sqrt{RR}},$$

the QT interval corrected for heart rate by the Fridericia's formula, QTcF, is defined as

$$QTcF = \frac{QT}{\sqrt[3]{RR}},$$

where RR represents the RR interval of the ECG, in seconds, and can be estimated as 60/Heart Rate.

Although Bazett's correction is the historical standard, it does not perform well when heart rate fluctuates. Fridericia's formula may perform better under these conditions. If QTcB and QTcF methods do not adequately correct for HR and there are a sufficient number of patients (eg >30) with baseline ECGs, an alternate correction to achieve the goal of getting uncorrelated QTc and RR is based on a linear regression methods which yields, theoretically, uncorrelated QTc and RR.

#### Linear regression method:

- Fit a model  $QT = a + b \times RR$  to baseline data
- Use the estimated slope,  $\hat{b}$ , to correct QT
- Corrected QT for heart rate will be computed as follows:

$$QTcP = QT + \hat{b} \times (1 - RR)$$

Data will be summarized using QTcF and QTcB. However, if these are not appropriate for the data set due to an observed large correlation between corrected QT and HR using the baseline assessments, the results will also be summarized using QTcP.

## ECG Summaries

The following analyses will be performed for each applicable ECG parameters (RR, PR, QRS, QT, ventricular rate -denoted as HR in what follows-, and QTc) by treatment group, during the on-treatment period. The denominator to calculate percentages for each category is the number of patients evaluable for the category

- Pearson correlation between QT and HR, QTc (QTcB, QTcF and, if applicable, QTcP) and HR using individual (non-averaged) baseline assessments
- For each of the ECG parameters (HR, and QT, QTc, QRS, PR intervals), descriptive statistics at baseline, at each post-baseline time point and changes from baseline at each post-baseline time point
- Frequency (number and percentage) of patients with notable ECG values according to the following categories:
  - QT/QTc increase from baseline >30 ms, >60 ms
  - QT/QTc > 450 ms, > 480 ms, > 500 ms
  - HR  $\leq$  50 bpm and decrease from baseline  $\geq$  20 bpm
  - HR  $\geq$  120 bpm and increase from baseline  $\geq$  20 bpm
  - PR  $\geq$  220 ms and increase from baseline  $\geq$  20 ms
  - QRS  $\geq$  120 ms

Patients with notable ECG interval values and qualitative ECG abnormalities will be listed for each patient and time point and the corresponding notable values and abnormality findings will be included in the listings.

Unscheduled ECG measurements will not be used in computing the descriptive statistics for change from baseline at each post-baseline time point. However, they will be used in the analysis of notable ECG changes and the shift table analysis of notable QT parameters.

### 6.6.8. Physical examination

Number and percentage of patients with abnormal findings in physical examination will be summarized by body system.

### 6.6.9. ECOG performance status

The ECOG shift from baseline to highest score during the on-treatment period will be summarized by treatment group. ECOG performance status with shift from ECOG=0 or 1 to ECOG 2 or higher will also be presented in a data listing.

## 7. INTERIM ANALYSES

Not applicable.

### **7.1. Introduction**

Not applicable.

### **7.2. Interim Analyses and Summaries**

Not applicable.

## 9. APPENDICES

### Appendix 1. Immune-Related Adverse Events

The MedDRA PTs and clusters for irAEs are defined in the Safety Review Plan (SRP) for avelumab.

Immune-related AEs (irAEs) will be programmatically identified as outlined in Table 8. This case definition is hierarchical, ie, each step is only checked for patients and events that have already met the prior step.

**Table 10. Case Definition for irAEs**

Step	Selection Criteria	Additional Notes
1	Event selected based on a list of pre-specified MedDRA PTs within clusters. These are included in the SRP as Tier1 events (Immune-mediated xxxx). If AE matches the list then it is in for the next step	
2	AE onset during 1 st study drug administration or anytime thereafter through 90 days after last dose of study treatment.	This is regardless of start of new anti-cancer drug therapy and regardless of TEAE classifications
3	Answer in the AE eCRF page to ‘Was another treatment given because of the occurrence of the event’ is ‘YES’	
4	AE treated with corticosteroids or other immunosuppressant therapy. For endocrinopathies only: AE required hormone replacement	Look in the conmed pages for AE identifiers that match the AEs from Step 3. For each of such AEs if A) OR B) below are met then the AE is in for the next step A) conmed ATC code is in (H02A, H02B, H02C, D07, A01AC, S01BA, S01BB, L04AA, L04AB, L04AC, L04AD, L04AX) and AE PT is in any of the irAE clusters. B) conmed ATC code is in (H03A, H03B) and AE PT is in one of the irAE clusters associated with “Immune-mediated endocrinopathies”

5
	
A) No clear etiology (other than immune mediated etiology)
 
B) Histopathology / biopsy consistent with immune-mediated event
 
Event is in if          [Answer to 5B1 and 5B2 is YES (regardless of answer to 5A)]          OR          [Answer to 5B1 is YES AND answer to 5B2 is NO AND answer to 5A is NO]          OR          [Answer to 5B1 is NO AND answer to 5A is NO]
	
A) From the AE eCRF page          Is the AE clearly related to an etiology other than immune-mediated etiology? Yes / No          If answer is Yes, check all that apply:
 
 
• Underlying malignancy / progressive disease.
 
• Other medical conditions.
 
• Prior or concomitant medications / procedures.
 
• Other. Specify.
 
 
B) From the AE eCRF page          B1) Was there a pathology /histology evaluation performed to investigate the AE? Y/N          B2) If answer to the above is Yes, does the pathology/histology evaluation confirms an immune mediated mechanism for the AE? Y/N          B3) If pathology / histology evaluation performed to investigate the AE, provide summary of relevant findings of the pathology /histology report. (Free Text)

----------	---	--

The data set associated with irAEs may be refined based on medical review. The final data set including any changes based on medical review (eg, addition of cases that are not selected by the programmatic algorithm) will be the basis of the irAE analyses.

